### **5.7.4 Safety Assessments**

Safety will be evaluated in terms of AEs, clinical laboratory results, vital sign measurements (blood pressure, heart rate, respiratory rate, and oral body temperature), safety 12-lead ECG results, and physical examination findings.

#### **5.7.4.1 Adverse Events**

##### **5.7.4.1.1 Adverse Event Definitions**

An AE is defined as any untoward and/or unintended sign, including an abnormal clinical laboratory finding, symptom, or disease temporally associated with the use of a study drug, whether or not considered related to the study drug. Events or conditions that increase in frequency or severity during or as a consequence of use of a drug in human clinical trials will also be considered AEs.

A treatment-emergent adverse event (TEAE) is defined as an AE that begins after study drug administration.

An unexpected AE is any AE having a specificity or severity not consistent with the current investigator's brochure for the study drug(s).

An SAE is defined as any AE occurring at any dose that meets the following criteria:

- Results in death,
- Is life threatening,

- Requires hospitalization or prolongation of existing hospitalization,
- Results in persistent or significant disability or incapacity,
- Is a congenital anomaly/birth defect, or
- Is an important medical event that may not meet the previous criteria but, based upon appropriate medical judgment, jeopardizes the subject or requires medical or surgical intervention to prevent one of the outcomes listed previously.

#### **5.7.4.1.2 Adverse Event Reporting**

The recording of AEs will begin after the subject signs the informed consent form and will continue until discharge (or early termination). All AEs, whether serious or nonserious and whether or not related to the study drug, must be recorded in the eCRF. Study subjects will be instructed to warn study staff if he or she has any unexpected symptoms. In addition, all subjects will receive a reminder telephone call approximately 24 hours before Check-in.

Any SAE (whether expected or unexpected) must be entered into the eCRF system and reported by facsimile to the medical monitor or designee using the SAE Reporting Form within 24 hours of the investigator or study clinic staff becoming aware of the event. It is the responsibility of the investigator to report all SAEs to the medical monitor, to provide the most complete report possible, and to assess each SAE for its relationship to the study drug. The investigator is responsible for obtaining follow-up information on all SAEs and submitting follow-up SAE data. Any unexpected SAEs must be reported promptly to the investigator's IRB as per the IRB's requirements.

In the event of a fatal or life-threatening SAE, the sponsor will notify the appropriate FDA authorities by telephone or facsimile within 7 calendar days of receipt of the report. The sponsor will follow all 7-day alert reports with a written report within 10 working days of receipt of the case. Serious AE cases that concern nonfatal, nonlife-threatening events that are unexpected and at least possibly related to the study drug will be submitted in writing to the FDA within 10 working days of receipt.

Furthermore, any AEs that are not expected, occur at a higher frequency, or would require modification of the study protocol and/or informed consent must be reported to the FDA within 10 working days.

Adverse events that are assessed by the investigator as possibly or probably related to the study drug will be followed until they resolve or stabilize. All SAEs will be followed until resolution.

#### **5.7.4.1.3 Assessment of Severity**

The investigator will assess the severity of each AE using the following scale:

- Mild: The subject is aware of the AE but is still able to perform all activities; minimal or no medical intervention or therapy is required.
- Moderate: The subject has to discontinue some activities due to the AE; minimal or no medical intervention or therapy is required.
- Severe: The subject is incapacitated by the AE and is unable to perform normal activities; significant medical intervention or therapy is required and hospitalization is possible.

#### **5.7.4.1.4 Assessment of Causality**

The investigator will assess the causal relationship/relatedness of each AE to the study drug using the following scale:

- Not Related: Onset of the AE has no reasonable temporal relationship to administration of the study drug, a causal relationship to administration of the study drug is biologically implausible, or the event is attributed to an alternative etiology.
- Unlikely Related: Onset of the AE has a reasonable temporal relationship to study drug administration and although a causal relationship is unlikely, it is biologically plausible.
- Possibly Related: Onset of the AE has a strong temporal relationship to administration of the study drug, cannot be explained by the subject's clinical state or other factors, and a causal relationship is biologically plausible.
- Probably Related: Onset of the AE shows a distinct temporal relationship to administration of the study drug that cannot be explained by the subject's clinical state or other factors, the AE is a known reaction to the product or chemical group, or can be predicted by the product's pharmacology.

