## **7.7. Safety Analyses**

### **7.7.1 Adverse Events**

All AEs will be coded using the latest version of the Medical Dictionary for Regulatory Activities. The incidence of TEAEs, organized by system organ class and frequency, will be summarized by seriousness, severity, relationship to treatment, and by treatment at onset of the TEAE. A detailed listing of serious AEs and TEAEs leading to withdrawal will also be provided.

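### The AE causality scale has no level for a plausible, well-timed event that also has a credible competing cause, and Probably Related can be read two ways

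*Protocol*

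**What the plan says.** Protocol 5.7.4.1.4 gives four levels.

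- **Not Related** lists three conditions, any one of which suffices. The last is "or the event is attributed to an alternative etiology".
- **Unlikely Related** asks for reasonable timing and adds: "although a causal relationship is unlikely, it is biologically plausible".
- **Possibly Related** joins three conditions with the word and: "Onset of the AE has a strong temporal relationship to administration of the study drug, cannot be explained by the subject's clinical state" or by other factors, and a plausible causal link.
- **Probably Related** opens with distinct timing that has no other explanation and continues: "the AE is a known reaction to the product or chemical group, or can be predicted by the product's pharmacology".

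Two parts of the plan use the rating in ways that matter here. Protocol 5.7.4.1.2 says: "Adverse events that are assessed by the investigator as possibly or probably related to the study drug will be followed until they resolve or stabilize". SAP 7.7.1, like Protocol 5.9.8.1, has the incidence of treatment-emergent events, which "will be summarized by seriousness, severity, relationship to treatment, and by treatment at onset of the TEAE".

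Protocol 5.7.4.1.2 also makes one FDA report depend on the rating: the written report, within 10 working days, of nonfatal, non-life-threatening SAEs that are unexpected and at least possibly related. The paragraph after it sets the same time limit for any AE that is unexpected, with no causality or seriousness condition.

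**The concern.** A graded causality scale needs a middle level for the ordinary uncertain case: the drug could have done it, but so could something else. Here the level named Possibly excludes that case, because it demands that nothing else explain the event. The level above repeats the demand.

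The uncertain case is not rare by design. Section 5.1.3 lists chills, fever and myalgia for both products and headache for Plegridy. Exclusion criterion 12 lists the same symptoms as possible signs of COVID-19. Section 5.8.9 bars caffeine from 48 hours before dosing and throughout the study, which gives headache another explanation. At stake are the follow-up that depends on the rating and the meaning of the relationship table.

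**Working it through.** The plan states no figure on this point, so the check sets the definitions and the rules that use them side by side.

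**Step 1. Place a test event.** Take an AE with good timing, a plausible mechanism and a credible competing cause, where causality is not judged unlikely and the alternative is not established as the cause.

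| Level | Neither known nor predictable reaction | Known or predictable reaction |
|---|---|---|
| Probably, parts read as alternatives | not met | met |
| Probably, parts read cumulatively | not met | not met |
| Possibly | not met: another explanation exists | not met: same reason |
| Unlikely | only if causality is judged unlikely | same |
| Not Related | only if attributed to the alternative | same |

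Read as alternatives, any one part of Probably is enough, so a known or predictable reaction qualifies whatever its timing or other causes. Read cumulatively, the final or joins only known and predictable, and the opening condition on timing and other explanations must also hold. In three of the four combinations of event type and reading, no level fits as written and the investigator can only move the event below Possibly.

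**Step 2. A concrete case.** Consider a Day 1 headache in a Plegridy recipient kept off caffeine. Read as alternatives, it is Probably Related. Read cumulatively, it is neither Probably nor Possibly, and it becomes Not Related if the investigator attributes it to caffeine withdrawal. The same facts can reach both ends of the scale.

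**Step 3. Trace what a rating below Possibly removes.**

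| Event or duty | Governing text | Effect of the lower rating |
|---|---|---|
| Nonserious AE, no discontinuation | Protocol 5.7.4.1.2 | follow-up to resolution or stabilisation lost |
| AE leading to discontinuation | Protocol 5.5 | follow-up kept |
| Any SAE | Protocol 5.7.4.1.2 | follow-up and 24-hour report to the medical monitor kept |
| Fatal or life-threatening SAE | Protocol 5.7.4.1.2 | 7-calendar-day FDA notice kept |
| Unexpected SAE, IRB report | Protocol 5.7.4.1.2 | kept |
| Unexpected, nonfatal, non-life-threatening SAE, FDA report | Protocol 5.7.4.1.2, two paragraphs | leaves the causality-based sentence; still caught by the next paragraph within 10 working days |
| Recording in the eCRF | Protocol 5.7.4.1.2 | kept |
| TEAE table by relationship | Protocol 5.9.8.1, SAP 7.7.1 | event moves to a lower row |

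Recording stops at discharge (Day 7 for groups A to C, Day 14 for D to G). The first row therefore matters in practice for events still unresolved at that point.

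**Step 4. Coarseness of the table.** Arm size is 12 (Protocol Table 5-1). One reclassified subject changes an arm's proportion by 1/12 = 0.083, or 8.3 percentage points. This describes any yes/no outcome in an arm of 12. It does not estimate how often misclassification would occur.

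**The case against.** The strongest reply is that little depends on the rating. All AEs are recorded, and all SAEs are followed and sent to the medical monitor. AEs that cause discontinuation are followed. Subjects are closely observed, with laboratory tests, an ECG and an examination at discharge. The relationship table is one descriptive cut among several. A placebo arm, with staff blind to treatment though not to route, allows AE incidence to be compared without any causality rating. The primary endpoints are neopterin metrics. All of this stands, and it limits the consequences to two.

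A reader might infer that expedited FDA reporting is lost. The documents do not support that: the unconditional paragraph in 5.7.4.1.2 covers unexpected AEs with the same time limit. What can be said is that the two paragraphs overlap, one with a causality condition and one without, and the protocol does not say how they fit together.

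A reader might also infer that the commonest reactions will be systematically under-attributed. That does not follow either. Under the alternatives reading, listed reactions are admitted to Probably, and so are unlisted ones that the pharmacology predicts. The direction of error for such events depends on the reading.

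Finally, the exclusion phrase calls for judgement: an alternative that merely exists need not explain the event. For COVID-19 the protocol provides a molecular test before admission and further testing when the investigator finds it necessary, so that alternative can often be checked. This reduces the number of uncertain cases, but it supplies no level for those that remain.

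**Conclusion.** The wording defect is real and its reach is narrow. Possibly and Probably share the no-other-explanation condition, the genuinely uncertain event has no level of its own, and the conjunctions in Probably allow two readings with opposite results. The supported consequences are lost follow-up to resolution or stabilisation for nonserious AEs that do not lead to discontinuation and are rated below Possibly, and a relationship table whose content depends on interpretation.

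Neither consequence can be quantified from the documents, which give no expected AE counts or rates of competing causes. The conclusion assumes that investigators apply the definitions as written; if they use a conventional middle category in practice, the effect shrinks. The point does not touch the primary analysis. It is worth correcting because a stated follow-up rule and a planned safety table both rest on this paragraph.

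**What to change.** Reword 5.7.4.1.4 so that the levels are ordered and mutually exclusive.

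- **Possibly:** remove the no-other-explanation condition. The event is well timed and biologically plausible, but could also be explained by clinical state or other factors. Say that this is permitted rather than required, so that a well-timed, unexplained event that is not yet a known or predictable reaction keeps its present place here.
- **Probably:** distinct timing AND not otherwise explained AND (a known reaction OR one predictable from the pharmacology), with the conjunctions written out.
- **Not Related and Unlikely:** state how firm the attribution to another cause must be, so that these levels do not overlap with Possibly. The documents do not dictate that threshold; the sponsor should set it.

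Rank the three timing terms (reasonable, strong, distinct) or reduce them to one. Align the eCRF help text. Reconcile the two FDA-reporting paragraphs in 5.7.4.1.2 so that it is clear whether causality is a condition. The SAP table needs no change.

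The cost is the rewording of one paragraph of definitions, a reconciliation of two others, the eCRF text, and the IRB approval that section 8.3.1 requires for an amendment. The downside is that somewhat more AEs will be classed as possibly related and followed up.

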#### **5.7.4.1.5 Pregnancy**

A serum pregnancy test will be performed for female subjects at the time points presented in the Schedules of Events (Table 9-1). If a subject becomes pregnant while on the study, this should be reported immediately to the investigator, the subject will be withdrawn from the study and the medical monitor and the subject will be instructed to follow-up with his or her personal physician. All pregnancies are to be reported as an AE and followed for outcome.

#### **5.7.4.2 Clinical Laboratory Tests**

Clinical laboratory and diagnostic screening tests will be performed at the time points presented in the Schedules of Events (Table 9-1) and will be collected in accordance with acceptable laboratory procedures. Clinical laboratory testing will be performed by will be

performed by the clinical study contractor. The clinical laboratory tests that will be performed are presented in Table 9-1. Unused clinical laboratory test samples will not be stored for future use.

**Table 5-2: Clinical Laboratory Tests and Diagnostic Screening Tests**

Hematology	Serum Chemistry	Urinalysis	Lipid Panel
Hematocrit Hemoglobin Platelet count Red blood cell count White blood cell count (with automated differential)	Alanine aminotransferase Albumin Alkaline phosphatase Aspartate aminotransferase Bicarbonate Bilirubin (total, direct, and indirect) Blood urea nitrogen Calcium Chloride Creatinine (including calculated creatinine clearance) Glucose Lactate dehydrogenase Magnesium Phosphorus Potassium Sodium Total protein Uric acid	Appearance Bilirubin Blood Color Glucose Ketones Leukocyte esterase Microscopic examination: red blood cells, white blood cells, epithelial cells, bacteria, crystals, and casts (if present) Nitrite pH Protein Specific gravity Urobilinogen	Total cholesterol High-density lipoprotein cholesterol (HDL-C) Low-density lipoprotein cholesterol (LDL-C) Triglycerides
Diagnostic Screening Tests:			
Serum	Urine	Other	
Serology (human immunodeficiency virus Ag/Ab Combo 1/2, hepatitis C virus antibody, and hepatitis B surface antigen) Female Subjects Only Human chorionic gonadotropin (for pregnancy)	Drug screen including: amphetamines, barbiturates, benzodiazepines, cannabinoids, cocaine, alcohol, opiates, phencyclidine, propoxyphene, and methadone	SARS-CoV2 molecular test	

Clinical laboratory results will be reviewed by the investigator or designee together with data in the eCRF. Any values outside the reference range will be evaluated for clinical significance. If a value is determined to be clinically significant, the subject will be instructed to follow-up with his or her personal physician. The investigator or designee may repeat the clinical laboratory tests if deemed appropriate. The investigator will maintain a copy of the laboratory accreditation and the reference ranges for the laboratory used.

#### **5.7.4.3 Vital Sign Measurements**

Vital signs (blood pressure, heart rate, respiratory rate, and oral body temperature) will be measured using an automated device at the time points presented in the Schedules of Events (Table 9-1). The subject should be in a supine position, if possible, for a minimum of 5 minutes before vital signs are measured.

#### **5.7.4.4 Safety 12-lead Electrocardiograms**

12-lead ECGs will be obtained with the subjects in the supine position for a minimum of 5 minutes before recording. ECGs will be overread by a physician. If an abnormality is observed, the subject will be instructed to follow-up with his or her personal physician.

#### **5.7.4.5 Physical Examinations**

A complete physical examination will be performed at the time points presented in the Schedules of Events (Table 9-1).

The complete physical examination will include, but not be limited to, assessments of the head, eyes, ears, nose, throat, skin, thyroid, nervous system, respiratory system, cardiovascular system, abdomen (liver and spleen), lymph nodes, and extremities. Height, weight (without shoes and wearing the lightest possible clothing), and calculation of body mass index will be performed at Screening only.

If a clinically relevant abnormality is observed upon physical examination, the subject will be instructed to follow-up with his or her personal physician.

#### **5.7.5 Demographics and Medical History**

Demographic data (date of birth, gender, race, and ethnicity) will be collected at Screening.

Each subject will provide a complete medical history at Screening that will be reviewed at Check-in. Specific information relating to any prior or existing medical conditions/surgical procedures will be recorded in the subject's eCRF.

## 5.8. Study Treatments

For each of the study drugs, doses were selected based on the doses studied in prior PK and/or PD studies. .

### 5.8.1 Treatments Administered

On Day 1 subjects will receive 1 of the following 7 treatments according to the randomization schedule:

- Treatment Group A: Avonex 7.5 µg IM
- Treatment Group B: Avonex 15 µg IM
- Treatment Group C: Avonex 30 µg IM
- Treatment Group D: Plegridy 31.25 µg SC
- Treatment Group E: Plegridy 62.5 µg SC
- Treatment Group F: Plegridy 125 µg SC
- Treatment Group G: Placebo, (6 subjects receive IM and 6 subjects receive SC)

Study drugs will be administered by a clinical research nurse on the study clinic floor at the subject's bedside. The pharmacist and investigator will be available if needed during study drug administration.

### 5.8.2 Dose Selection

#### 5.8.2.1 Avonex

The high dose for beta-interferon is 30 µg, which is the clinical dose. The mid-dose is 15 µg and the low dose is 7.5 µg. The dose selection rationale is based on available data for the PK and PD dynamic range of beta-interferon. This dose range will cover the sensitive dose-area-under-the effect curve (AUEC) relationship and dose- $E_{max}$  (nadir) relationship of the PD response (neopterin). Doses within the study range and greater have been safely administered to healthy subjects.

#### 5.8.2.2 Plegridy

The high dose for PEG-beta-interferon is 125 µg, which is the clinical dose. The mid-dose is 62.5 µg and the low dose is 31.25 µg. The dose selection rationale is based on available data for the PK and PD dynamic range of PEG-beta-interferon. This dose range will cover the sensitive dose-area-under-the effect curve (AUEC) relationship and dose- $E_{max}$  (nadir) relationship of the PD response (neopterin). Doses within the study range and greater have been safely administered to healthy subjects.

### **5.8.3 Method of Assigning Subjects to Treatment Sequence**

#### **5.8.3.1 Randomization Process**

The project biostatistician will create the specifications that will be used to generate the randomization schedule. The specifications will be based on the protocol requirements and appropriate statistical programming with consideration for study design, number of treatments, number of subjects planned for enrollment, stratification, and blocking.

Based on these specifications, the project biostatistician (or designee) will generate a dummy randomization schedule. The schedule is generated using R.

The project biostatistician (or designee) distributes the ‘dummy’ randomization schedule to specified personnel for review. Any change (e.g., change in block size, change in stratification levels) that requires an update to the specifications will reset this process. Minor changes (e.g., display formatting) will not require a change to the specifications.

After the approval of the ‘dummy’ randomization schedule, the project biostatistician (or designee) transfers the program used to generate the ‘dummy’ schedule to the randomization biostatistician (unblinded), who is an independent party and will not be participating in any programming or statistical decisions for the study before breaking the blind. No transfer is necessary if the unblinded randomization biostatistician also created the ‘dummy’ randomization.

The randomization biostatistician is responsible for generating the final randomization schedule. The output is sent only to designated unblinded recipients, who will maintain a secured digital and printed copy for their use.

Archival of the programs and output is accomplished by the creation of an encrypted, password-protected ZIP file containing the program and output file(s). The ZIP file is copied to a storage drive at the sponsor’s site.

Randomization will occur after informed consent is obtained, either after completion of check-in procedures on Day -1 or just before dosing on Day 1. Approximately 84 healthy male and female subjects are planned for enrollment. Unique subject numbers will be used in sequential order based on each subject’s order of qualification.

Enrolled subjects will be randomly assigned to 1 of 7 different treatment groups. The treatment groups are presented in Table 5-3.

**Table 5-3: Study Treatment Groups**

Subjects (n)	Treatment Group	Drug
12	A	Interferon beta-1a (Avonex) low (7.5 µg)
12	B	Interferon beta-1a (Avonex) intermediate (15 µg)
12	C	Interferon beta-1a (Avonex) high (30 µg)
12	D	Peginterferon beta-1a (Plegridy) low (31.25 µg)
12	E	Peginterferon beta-1a (Plegridy) intermediate (62.5 µg)
12	F	Peginterferon beta-1a (Plegridy) high (125 µg)
12	G	Placebo

All randomization information will be secured and housed in a locked storage area, accessible only by the randomization personnel and the assigned pharmacist and his or her verifier.

